**PROTOCOL SUMMARY**

Full Title	Effect of Continuous Positive Airway Pressure (CPAP) treatment on cognitive ability in HIV+ individuals with obstructive sleep apnea (OSA): A pilot study
Short title	HIV and CPAP
Sponsor	McGill University
Funding	Canadian Institute of Health Research (CIHR) CPAP and masks for the duration of the study are provided in-kind by Resmed and cost of visits related to its initiation and calibration are provided in-kind by VitalAire
Principal Investigators	[name], [name], [name]
Associate investigators	[name], [name]
Objectives	
The primary objective is to estimate among people with HIV and obstructive sleep apnea, the extent to which 4-7 months of CPAP impacts on the primary outcome of cognitive ability (B-CAM), in comparison to individuals who screen positive for OSA but are not participating in the sleep apnea intervention.
 
An exploratory objective is to identify whether the changes are similar on measured cognitive ability and on self-reported cognitive symptoms.
 
The explanatory objective is to relate degree of adherence to CPAP to change in cognitive outcomes.

Study Population	
Inclusion Criteria
 

• Participants in the cohort study “Understanding and Optimizing Brain Health in HIV Now”

• Screened positive for OSA using the Berlin or the STOP-BANG (completed as part of the main study visits)

• Have been on a stable HAART regimen for > 6 months

• B-CAM ≤ 29

• Have not had a change in medications that could potentially interfere with sleep or cognition in the past 4 months.

• Willing to use CPAP as per instructions

• Able to comply with follow-up visit assessments

• Able to communicate in English or French

• Have at least one remaining visit in the main cohort study

 
Exclusion Criteria
 

• Already treated for OSA

**Effect of Continuous Positive Airway Pressure (CPAP) treatment on cognitive ability in HIV+ individuals with obstructive sleep apnea (OSA): A pilot study**

	

• Ongoing involvement in night shift work

• Presence of restless legs syndrome requiring immediate specific treatment

Study Design	Quasi-experimental single-arm, pre-post design will be carried out over a period of 4-7 months.
Sample Size	30 participants have used the CPAP device for a minimum of 4 months, on at least 30% of the nights with a median use of $\geq 4$ hours/night.
Participant involvement	Up to 12 months

## **Effect of Continuous Positive Airway Pressure (CPAP) treatment on cognitive ability in HIV+ individuals with obstructive sleep apnea (OSA): A pilot study**

### **BACKGROUND**

Cognition and HIV: People living with HIV worry about their memory, and with good reason. As their life expectancy increases, it is becoming clear that this chronic illness affects cognition, even with excellent systemic viral control. The cognitive disturbances observed in HIV infection fall under the broader term HIV-associated neurocognitive disorders (HAND). Although the prevalence of HAND in Canada is unknown, it is likely to be high. Recent studies in other developed countries report a prevalence of cognitive impairment of 30-50% [1, 2]. Even higher rates have been documented in those over the age of 50, a rapidly expanding group.

There is currently no treatment for HAND. However, it is now recognized that HIV infection is associated with several medical conditions that independently contribute to cognitive disturbances. Identification and treatment of potentially reversible contributors to cognitive impairment is therefore key to the clinical management of these cognitive difficulties.

Definition of obstructive sleep apnea: Obstructive sleep apnea (OSA) is a breathing disorder that is characterized by episodes of complete or partial cessation of respiration during sleep, associated with upper airway collapse, oxygen desaturation and sleep fragmentation [3]. The index commonly used to assess sleep disordered breathing (SDB) is the respiratory disturbance index (RDI), defined as the average number of respiratory disturbances (obstructive apneas, hypopneas, and respiratory event-related arousals [RERAs]) per hour. According to the Centers for Medicare & Medicaid Services criteria for the positive diagnosis and treatment of obstructive sleep apnea, a positive test for OSA is established if the RDI  $\geq 15$  events per hour [4].

Obstructive sleep apnea and cognition: Obstructive sleep apnea (OSA) is a condition frequently implicated in cognitive disturbances [3, 5-10]. These cognitive deficits are common : for example, in a meta-analysis of individuals with OSA, information processing speed was reduced in as many as 75% of individuals compared with norm-referenced data [6]. In addition to its negative impact on cognition, OSA is associated with health conditions such as hypertension, metabolic disturbances (including impaired glucose tolerance, insulin resistance and dyslipidemia) and heightening risk of heart disease, stroke and mortality [11-13], conditions also increased in persons living with HIV. Individuals suffering from OSA report an increase in daytime sleepiness, mood changes and decline in quality of life [6-10]. OSA also portends economic and societal impact through lost productivity at work and motor vehicle accidents [14]. The presence of OSA is therefore important to detect in those living with HIV as it is a potentially treatable contributors to cognitive disturbances in HIV.

Obstructive sleep apnea and HIV: General population estimates of moderate to severe sleep-disordered breathing depend on criteria used and vary widely [15], from 6-13% of individuals [6, 16], to up to 23% of women and 50% of men [17] using modern criteria. This prevalence is increased in the HIV population. Based on data from the Multicenter AIDS Cohort Study (MACS, N=1896) and Women's Interagency HIV Study (WIHS, N=1976), HIV-infected individuals are more likely to be diagnosed with OSA than HIV-uninfected individuals when confounders such as age and body mass index were accounted for (Prevalence Ratio (PR) 1.42; p=0.01 and PR 2.10; p=0.002, respectively)

## **Effect of Continuous Positive Airway Pressure (CPAP) treatment on cognitive ability in HIV+ individuals with obstructive sleep apnea (OSA): A pilot study**

[18]. HIV-infected individuals have many risk factors for OSA including a high rate of obesity: >60% of HIV-infected women in the WIHS and >40% of HIV-infected men and MACS [19].

Traditional risk factors associated with OSA include advanced age, male gender, large neck circumference, obesity and hypertension [13]. However, these traditional clinical indicators of OSA may be less salient in the presence of HIV infection. In a large observational study, those with HIV and OSA were more likely to be younger, have lower body-mass-indexes and were less likely to have hypertension than those without HIV infection [20]. As a result of this different risk profile, the presence of OSA in HIV+ individuals was more often undiagnosed [20], underscoring the need for a higher index of suspicion in the presence of HIV infection.

Treatment of obstructive sleep apnea and its impact on cognition: Continuous Positive Airway Pressure (CPAP) is the recommended treatment of choice for OSA. A CPAP device includes a pump which delivers air via a mask covering the nose or mouth while a person is sleeping [21]. The flow of air generates positive pressure, which opens the airways, preventing soft tissue collapse [21].

CPAP has established efficacy in improving cognition. A meta-review involving review articles meeting pre-determined strict criteria, concluded that CPAP use improved executive function, long-term verbal and visual memory, attention/vigilance and global cognitive functioning [22]. Another meta-analysis also found that individuals with OSA demonstrated medium to very large impairments executive dysfunction, independent of age and disease severity, which showed small to moderate improvements following CPAP treatment [23]. In the context of Alzheimer's disease, Ancoli-Israel et al. conducted a randomized double-blind placebo-controlled trial to determine whether CPAP use resulted in improvements in neuropsychological test scores. Although the study was underpowered to make definitive conclusions about improvements within specific cognitive constructs, exploratory post hoc examination of score changes suggested that CPAP use by individuals with OSA yielded some benefits; these included improvements in episodic verbal learning and memory and some aspects of executive functioning such as cognitive flexibility and mental processing speed [24].

Although CPAP has been associated with improvements in cognitive functioning in the general population, its effectiveness in improving cognition in HIV+ individuals has never been previously tested. Given that the cognitive disturbances in this population are multi-factorial, determining whether treatment of OSA in this population improves cognition is key in improving the clinical management of HIV+ individuals, both for its negative impact on cognition but also more generally for their health.

Obstructive sleep apnea in the cohort “Understanding and Optimizing Brain Health Now”. Cohort participants (N=840) are studied prospectively over a 27-month period with visits every 9 months. Patients complete a computer-based evaluation of cognitive ability, the B-CAM, as well as questionnaires on socio-demographic characteristics, symptom status, functional status, health perception and quality of life. Given the high prevalence of OSA reported in the population, participants complete questions that, combined with other values already documented, support the scoring of two screening questionnaires for OSA, the Berlin [25, 26] and the STOP-BANG [27, 28] (see

## **Effect of Continuous Positive Airway Pressure (CPAP) treatment on cognitive ability in HIV+ individuals with obstructive sleep apnea (OSA): A pilot study**

Appendix 1). Selected cohort members at the Montreal sites who screen positive for the presence of OSA will be invited to participate in the study.

### **STUDY OBJECTIVES**

The overall aim is to contribute evidence about the impact of treatment of sleep apnea (with CPAP) on cognitive ability in HIV+ individuals.

The primary objective is to estimate among people with HIV and obstructive sleep apnea, the extent to which 4-7 months of CPAP impacts on cognitive ability (B-CAM), in comparison to individuals who screen positive for OSA but are not participating in the sleep apnea intervention.

An exploratory objective is to identify whether the changes are similar on measured cognitive ability and on self-reported cognitive symptoms.

The explanatory objective is to relate degree of adherence to CPAP to change in cognitive outcomes.

### **STUDY HYPOTHESIS**

Given there is no expectation for improvement in cognitive ability in this population in the absence of treatment for sleep apnea, we hypothesize that, over 4-7 months weeks of CPAP use, an improvement in cognition will occur, and if this is observed in 7 or more of 30 people, this response frequency is unlikely to have occurred by chance.

### **STUDY DESIGN**

This study is part of a larger project based upon a cohort multiple randomized controlled design [29]. Within a fully characterized cohort (N=840) which is followed over time, people meeting the specific criteria for one or more interventions (here CPAP) are identified and a sample is randomly selected to receive the intervention; the remaining eligible persons who do not receive the intervention serve as controls. This design, when operationalized for one intervention, yields three cohorts: (i) the intervention cohort comprising all those approached who agreed to enter; (ii) the refuser cohort comprising all those approached who declined entry; and (iii) control cohort comprising eligible persons who were not approached, and hence were not given the opportunity to accept or decline. For the CPAP intervention, the duration of the study is 4-7 months.

Eligible patients will be identified among the Montreal participants (N=500) in the “Understanding and Optimizing Brain Health Now” cohort study who have screened positive for the possible presence of sleep apnea on either the Berlin or the STOP-BANG and experience some cognitive difficulties as measured by the B-CAM ( $\leq 29$ ). We will continue recruitment until 30 participants have used the CPAP device for a minimum of 4 months, on at least 30% of the nights with a median of  $\geq 4$  hours/night.

### **Eligibility criteria**

#### **Inclusion criteria**

- Participants in the cohort study “Understanding and Optimizing Brain Health in HIV Now”

## **Effect of Continuous Positive Airway Pressure (CPAP) treatment on cognitive ability in HIV+ individuals with obstructive sleep apnea (OSA): A pilot study**

- Screen positive for the presence of OSA with either the Berlin or the STOP-BANG
- Have been on a stable HAART regimen for > 6 months
- B-CAM score ≤ 29
- Have not had a change in medications that could potentially interfere with sleep or cognition in the past 4 months.
- Willing to use CPAP as per instructions
- Able to comply with follow-up visit assessments
- Able to communicate in English or French
- Have at least one remaining visit in the main cohort study

### **Exclusion criteria**

- Already treated for OSA
- Ongoing involvement in night shift work
- Presence of restless legs syndrome requiring immediate specific treatment

### **Screening:**

Brain Health Now study participants who screen positive for the presence of OSA, meet inclusion/exclusion criteria based on the information already available as part of the main study questionnaires and who, on initial enrolment, have agreed to be contacted for sub-studies, will be approached for participation. Those who agree to participate and provide informed consent will be referred for a polysomnography (sleep study). Those with confirmed OSA will continue to the intervention phase.

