## **Effect of Continuous Positive Airway Pressure (CPAP) treatment on cognitive ability in HIV+ individuals with obstructive sleep apnea (OSA): A pilot study**

The values to be used will be those collected during the scheduled platform evaluations which occur 9-12 months apart.

- (ii) Self-reported cognitive symptoms will be measured using the C3Q (Communicating Cognitive Concerns in HIV) collected during the scheduled platform evaluations which occur 9-12 months apart.
- (iii) Adherence to the CPAP home treatment will be obtained from the CPAP device directly through its telemonitoring function, which is done by activating modems on CPAP machines and having the data transferred onto the Compliance Management Solutions. The granularity of the data will yield a continuous metric of sleep-minutes of use. Reasons for poor adherence and tolerance will be obtained by telephone contact or at clinical visits with the sleep specialist.
- (iv) Three cohorts will be compared: (i) the intervention cohort comprising all those approached who agreed to enter; (ii) the refuser cohort comprising all those approached who declined entry; and (iii) control cohort comprising eligible persons who were not approached, and hence were not given the opportunity to accept or decline.

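### The Screening section omits the random selection on which the Study Design rests, and agreement to sub-study contact limits who can be approached but not who can be a control

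*Protocol*

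**What the plan says.** Study Design places the trial in a cohort of 840 with several embedded interventions. Among people meeting the criteria, "a sample is randomly selected to receive the intervention; the remaining eligible persons who do not receive the intervention serve as controls". It then defines three cohorts: those approached who agreed, those approached who declined, and a "control cohort comprising eligible persons who were not approached, and hence were not given the opportunity to accept or decline". The Measurement section repeats these definitions. Recruitment is from the 500 Montreal participants and has a stopping rule: "We will continue recruitment until 30 participants have used the CPAP device for a minimum of 4 months", with a minimum level of use.

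The Background states: "Selected cohort members at the Montreal sites who screen positive for the presence of OSA will be invited to participate in the study". It does not say how they are selected.

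The Screening section is the operational instruction. Members who screen positive, satisfy the criteria on data already held and "have agreed to be contacted for sub-studies, will be approached for participation". No draw, ordering or held-back group is mentioned.

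The eligibility lists in the Protocol Summary and under Eligibility criteria do not include agreement to sub-study contact. Statistical Analysis and Sample compares the three cohorts by linear GEE adjusted for age, sex, education, BMI and comorbidity, and expects far more controls than intervention participants.

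**The concern.** In this design, the comparison is credible only if the people approached and the people not approached come from one eligible pool and are separated by chance. Two features of the text work against that.

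First, the section that staff would follow when inviting people contains no chance step. If they work through the list by visit date, clinic or convenience, the people left over when recruitment stops are whoever came late in that order.

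Second, willingness to be contacted acts as a filter on one side only. Everyone approached has passed it. The controls need not have, because the control definition asks only that a person be eligible and not approached. Someone who declined sub-study contact meets that definition automatically. Willingness to take part in research may well go with motivation, health or cognitive course, and it is not among the GEE covariates.

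At stake is the between-cohort estimate. The primary objective is worded as a comparison with screen-positive people who are not in the intervention, so this estimate serves a stated primary aim.

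**Working it through.** The point is textual, so the first step is to set the sections side by side.

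| Element | Study Design / Measurement | Screening | Eligibility lists |
|---|---|---|---|
| How people are chosen for approach | Random sample of those meeting criteria | No sampling step stated | Not addressed |
| Agreement to sub-study contact | Not mentioned | Required before approach | Not mentioned |
| Who is a control | Eligible and not approached | Not addressed | Not addressed |

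Two consequences follow.

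1. A person who is eligible but declined contact has zero chance of being approached. By definition that person falls into the control cohort. This holds even if a perfect random draw is made among contactable people.
2. The remaining controls are contactable people not reached when recruitment stopped. They are a random remainder only if the order of approach was random, and Screening does not say so.

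**Can the bias be sized?** Let *s* be the share of controls who could never have been approached, and *d* the difference between their expected B-CAM change and that of contactable controls, given the GEE covariates. The shift in the control mean is *s* × *d*. The Protocol gives neither.

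To show how loosely *s* is fixed, take these inputs, all assumed except the 500: 20% of the 500 Montreal members eligible (100 people), 80% or 95% of them contactable, controls drawn from Montreal only, and a yield *y* of adherent users per person approached.

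- Number to approach = 30 / *y*: 50 at *y* = 60%, 75 at 40%, 150 at 20%.
- Contactable people left = contactable − approached, with a floor of zero.
- *s* = non-contactable / (non-contactable + contactable left).

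| Yield (assumed) | 80% contactable (20 not contactable) | 95% contactable (5 not contactable) |
|---|---|---|
| 60% (50 approached) | 30 left; *s* = 20/50 = 40% | 45 left; *s* = 5/50 = 10% |
| 40% (75 approached) | 5 left; *s* = 20/25 = 80% | 20 left; *s* = 5/25 = 20% |
| 20% (150 needed) | pool exhausted, 0 left | pool exhausted, 0 left |

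So *s* runs from 10% up to the whole control cohort on inputs that the Protocol does not exclude. It would be lower with a larger eligible pool, higher contact agreement or controls from other sites. Since *d* is wholly unknown, no figure for the bias can be defended.

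**What is not touched.** The responder rule uses only CPAP participants. With 30 people and a 10% response rate, P(7 or more) = 0.0258 and P(6 or more) = 0.0732, so 7 is the right cut-off for p < 0.05. The make-up of the control cohort does not enter.

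**The case against.** The strongest reply is that Screening states a precondition for being approached, and that the selection is stated elsewhere. Study Design says that people "are identified and a sample is randomly selected to receive the intervention", and the Background speaks of selected members. On that view the sections fit together and one sentence is merely incomplete. This stands in part: the intention to sample is clear. But no section says how the draw or order is made, and reading the sections together does nothing about contact agreement, which is still missing from the control definition.

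A reader might go further and infer that every eligible, contactable person is approached, so that the controls are only people who declined contact. The documents do not support that. Screening does not say that all are approached, the Background says that selected members are invited, and the stop at 30 adherent users can leave contactable people unreached. The analysis section also expects a control cohort far larger than the intervention cohort, and controls are not expressly confined to Montreal.

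It is also fair to say that the intervention cohort is self-selected in any case. It consists of people who accepted, and those who go on to CPAP have OSA confirmed by polysomnography. The Protocol Summary calls the design quasi-experimental and single-arm. This limits what a repair can achieve. It does not justify adding a further avoidable difference between approached and unapproached people.

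**Conclusion.** The concern holds as a gap in two definitions. The approach rule lacks the random step that Study Design claims, and agreement to contact restricts the approached cohorts but not the controls. The effect is confined to the between-cohort GEE; the 7-of-30 rule stands as it is. The size and direction of the bias are unknown. It could be negligible if few people declined contact and many contactable people remain unapproached, and the table above shows only that the Protocol does not settle this. The conclusion rests on the wording alone and needs none of the assumed rates. The change is worth making because the affected comparison is the one named in the primary objective and the repair is small.

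**What to change.** 1. Add agreement at cohort enrolment to sub-study contact as a condition for all three cohorts, in the eligibility lists and in the cohort definitions under Study Design and Measurement.
2. Amend Screening so that eligible, contactable Montreal members are put in random order and approached in that order until the recruitment target is met. Those not reached form the control cohort.

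The cost is a few sentences, a random ordering of a list, and a somewhat smaller control cohort, because people who declined contact leave it. As worded, the change also excludes the 840 − 500 = 340 cohort members outside Montreal. If the sponsor meant to use eligible people among them as controls, the Protocol should say so and report them separately. The sponsor should also count the eligible, contactable members from cohort data beforehand, since a low yield could exhaust the pool before the target is met and leave few or no controls.

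The change makes approached and unapproached people comparable. It does not make CPAP accepters versus controls a randomised contrast, and the report should not present it as one.
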